- After 3 months of treatment with OCTA101, the patients had their 3-month follow-up visit. During the 2 to 3 weeks waiting for all relevant results, especially FVIII inhibitor testing results, these patients continued on daily dosing with 12.5 IU/kg OCTA101 sc.
- DMC agreed that further patients can start their daily prophylaxis with OCTA101, up to 16 patients proceeded with 12.5 IU/kg OCTA101. After further 3 months, following DMC data review, the first 3 patients of this cohort were planned to start on daily dosing with 25 IU/kg OCTA101 sc for 6-7 months. The remaining patients were planned to follow after a further 3 months, after DMC data review.
- Patients reporting two spontaneous bleeding episodes will be switched to the next higher dose level after having completed at least 3 months with 12.5 IU/kg OCTA101 daily treatment: they will start daily dosing with 25 IU/kg OCTA101 sc.

Name of Sponsor/Company: Octapharma AG		
Name of Investigational Product: OCTA101 (Human-cl rhFVIII and recombinant human von Willebrand Factor fragment dimer)	Protocol Identification Code: SubQ8-01	silor
Name of Active Ingredient: Coagulation factor VIII	Date of Final Protocol: 30-Jul-2021	

- Depending on the results of the 12.5 IU/kg and 25 IU/kg OCTA101 treatment phases, the initiation of a 40 IU/kg OCTA101 phase will be considered together with the DMC.
- Bleeding episodes will be controlled with the use of Nuwiq during the entire duration of treatment in Cohort 6.

The cohorts are summarized as follows:

• Cohort 1: 50 IU/kg OCTA101 (n=4): Single-period investigation with a single sc dose of 50 IU/kg OCTA101 profiled up to 72 hours after dosing.

DMC assessment after last patient of Cohort 1. If ok, proceed with Cohort 2, and also with daily prophylactic dosing (approximately 40-60 IU/kg) for 3 months (initially with Nuwiq but then with OCTA101 if advised by the DMC). Patients from Cohort 2 and 3 may also start their daily prophylactic dosing for 3 months immediately after collection of the last PK sample.

- Cohort 2: 100 IU/kg OCTA101 (n=4): Single-period investigation with a single sc dose of 100 IU/kg OCTA101 profiled up to 96 hours after dosing. DMC assessment after last patient of Cohort 2. If ok, proceed with Cohort 3.
- Cohort 1 and 2: PK assessment after 3-month daily dosing (n=8): single-period investigation with a single sc dose of 50 IU/kg OCTA101 profiled up to 120 hours after dosing for FVIII and up to 21 days for OCTA12.

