The total annualized bleeding rate, the spontaneous annualized bleeding rate, the traumatic annualized bleeding rate, the total annualized treated bleeding rate, the spontaneous annualized treated bleeding rate, and the annualized joint bleeding rate during the daily sc treatment with OCTA101 will be presented for patients in the FAS and PP set in Cohort 6, grouped by dose level of daily OCTA101 dosing. These bleeding rates will be compared descriptively to those derived from the bleeding frequencies in the previous 6 months prior to the study. For the daily dosing period of Cohorts 1 to 3, no bleeding rates were calculated, because none occurred during daily prophylaxis with OCTA101. The observation period was considerably shorter than planned due to the study stop.

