In order to evaluate the safety, efficacy, and PK of OCTA101 after repeated doses, with the revised study design, patients from Cohort 1, 2, and 3 received daily dosing (approximately 40-60 IU/kg, with the dose chosen to allow administration by a single injection; it was permitted to daily alternate the vial size, e.g. 3000 IU on one day 1, 5000 IU on day 2, 3000 IU on day 3, 5000 IU on day 4 etc.) of OCTA101 for 3 months. A new cohort will also investigate 12.5 IU/kg OCTA101 sc daily for 6-7 months and with DMC agreement at each stage, the patients will then proceed to 25 IU/kg (and probably 40 IU/kg) OCTA101 sc daily for a further 6-7 months. Throughout the prophylaxis parts of the study, FVIII inhibitors (including LumiTope assay), plasma concentrations of FVIII:C, and OCTA12 will be measured repeatedly. Bleeding episodes should be treated with Nuwiq.

As discussed in the Benefit-Risk Statement below, based on the accumulated data from the study, an additional cohort, Cohort 6, will investigate lower doses of 12.5 and 25 IU/kg (and probably 40 IU/kg) OCTA101 sc daily for 6-7 months each, based on DMC recommendations.

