A new cohort (Cohort 6) was planned with 16 evaluable patients. In this cohort, around 18-20 patients (to compensate for possible early drop-outs) were planned to start with an initial 4 to 6-week run-in treatment period with Nuwiq iv prophylaxis followed by 12.5 IU/kg OCTA101 sc daily prophylaxis for >3 up to 6-7 months. With DMC agreement, the patients were planned to proceed to 25 IU/kg OCTA101 sc daily prophylaxis for 6-7 months. Based on the results of both dosing phases, a 40 IU/kg OCTA101 were planned to be considered.

Cohort 6 was planned to proceed as follows:

Propert

Following completion of the run-in period with Nuwig iv prophylaxis, 3 patients (one • screened patient withdrew consent after Nuwiq run-in phase) started daily dosing with 12.5 IU/kg OCTA101 sc.

Study Protocol No. SubQ8-01, Version 9.0 CONFIDENTIAL

- After 3 months of treatment with OCTA101, the patients will have their 3-month followup visit. During the 2 to 3 weeks waiting for all relevant results, especially FVIII inhibitor testing results, these patients will continue on daily dosing with 12.5 IU/kg OCTA101 sc.
- If the DMC determines that further patients can start their daily prophylaxis with OCTA101, at least 16 patients will proceed with 12.5 IU/kg OCTA101. After a further 3 months, following DMC data review, the first 3 patients of this cohort will start on daily dosing with 25 IU/kg OCTA101 sc for 6-7 months. The remaining patients will follow after a further 3 months, after DMC data review.
- Patients reporting two spontaneous bleeding episodes will be switched to the next higher dose level after having completed at least 3 months with 12.5 IU/kg OCTA101 daily treatment: they will start daily dosing with 25 IU/kg OCTA101 sc.
- Depending on the results of the 12.5 IU/kg and 25 IU/kg OCTA101 treatment phases, the initiation of a 40 IU/kg OCTA101 phase will be considered together with the DMC.
- Bleeding episodes will be controlled with the use of Nuwig during the entire duration of treatment in Cohort 6.

The cohorts are summarized as follows:

- Cohort 1: 50 IU/kg (n=4): single-period investigation with a single sc dose of 50 IU/kg OCTA101 profiled up to 72 hours after dosing.
- Cohort 2: 100 IU/kg (n=4): single-period investigation with a single sc dose of 100 IU/kg OCTA101 profiled up to 96 hours after dosing.

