#### **Dose and Dosing Schedule** 5.4

The following will be administered at the study site by trained personnel:

Cohort 1: Single injection of OCTA101 50 IU/kg sc with 72 hours of observation.

- Cohort 2: Single injection of OCTA101 100 IU/kg sc with 96 hours of observation.
- Cohort 1 and 2: PK assessment after 3-month daily dosing: Single injection of OCTA101 50 IU/kg sc with 120 hours of observation for FVIII and 21 days of observation for OCTA12.
- Cohort 3: Single injection of Nuwiq 50 IU/kg iv with 72 hours of observation, followed by single injection of OCTA101 50 IU/kg sc administered into the abdomen with 72 hours of observation.
- Cohort 4: (Cancelled) Single injection of OCTA101 50 IU/kg sc administered into the thigh with 72 hours of observation.
- Cohort 5: Single injection of OCTA101 20 IU/kg sc with 72 hours of observation, followed by single dose of OCTA101 40 IU/kg sc with 72 hours of observation, followed by single dose of OCTA101 60 IU/kg sc with 72 hours of observation.
- Cohort 6: 4-6 weeks prophylactic run-in treatment phase with ~30 IU/kg Nuwiq iv, given 3 x weekly, followed by 2 (probably 3) phases of 6-7 months daily injection with OCTA101, first 12.5 IU/kg, followed by 25 IU/kg daily (and probably 40 IU/kg). No wash-out periods are required between the treatment phases. Patients reporting two spontaneous bleeding episodes during the 12.5 IU/kg treatment phase may immediately switch to the 25 IU/kg daily, if they have completed at least 3 months with 12.5 IU/kg. Nuwiq (according to SmPC) is used to control bleeding episodes, if any.

In all cases, the minimum number of injections required to provide the required dose must be administered. If multiple injections are needed, then they should not be administered at the same spot. The PK doses were to be achieved as accurately as possible with the available vial strengths as a single injection; it was permitted to daily alternate the vial size, (e.g. 3000 IU on one day 1, 5000 IU on day 2, 3000 IU on day 3, 5000 IU on day 4 etc.).

OCTA101 will be administered by sc injection into the abdomen or thigh (see Appendix 1 in Section 13.a), whereby for Cohorts 1 and 2 the choice is up to the investigator and patient, in Cohort 3 all administrations of OCTA101 will be into the abdomen, in Cohort 5, four patients each will consistently be injected with OCTA101 either in the abdomen or in the thigh at all three dose levels.

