The total annualized bleeding rate, the spontaneous annualized bleeding rate, the traumatic annualized bleeding rate, the total annualized treated bleeding rate, the spontaneous annualized treated bleeding rate, and the annualized joint bleeding rate during daily se treatment with OCTA101 will be presented for patients in the FAS and PP set in Cohort 6, grouped by dose level of daily OCTA101 dosing. For the daily dosing period of Cohorts 1 to 3, no bleeding rates were calculated. The observation period was considerably shorter than planned due to the study stop. Bleedings occurred only in patients who had developed antibodies or after the end of the daily dosing period.

All other data collected for BEs, efficacy assessments at the end of BEs will be analyzed descriptively. The proportion of BEs successfully treated with Nuwiq will be presented. Summaries on patient levels will be detailed in the SAP as needed. All data collected will be listed.

FVIII:C and OCTA12 trough and peak plasma levels during daily dosing will be analyzed descriptively.

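### Cohort 6: the step to 25 IU/kg is gated on DMC review, but the protocol does not say whether the bleed-triggered switch to that dose is under the gate, or whether it is required or optional

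*Protocol*

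**What the plan says.** **Planned route to 25 IU/kg.** The Study Outline (Study Design) and Section 1.4 make the step from 12.5 to 25 IU/kg conditional on the DMC. Section 1.4 puts it as "with DMC agreement at each stage, the patients will then proceed to 25 IU/kg", with no exception. The Study Outline and Section 3.2 add the staging: the first three patients go up after a DMC data review, and for the others "The remaining patients will follow after a further 3 months, after DMC data review".

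**Bleed-triggered route to 25 IU/kg.** In the Study Outline: "Patients reporting two spontaneous bleeding episodes will be switched to the next higher dose level", once 3 months at 12.5 IU/kg are complete. Section 3.2 repeats this as an instruction. The cohort summary and Duration of Treatment in the Study Outline also state the increase as definite; the cohort summary in Section 3.2 calls it planned. Section 5.4 makes it permissive: "Patients reporting two spontaneous bleeding episodes during the 12.5 IU/kg treatment phase may immediately switch to the 25 IU/kg daily", again once 3 months at 12.5 IU/kg are complete.

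Every version has the same two conditions, two spontaneous bleeds and 3 months at 12.5 IU/kg. None mentions the DMC, release of the 25 IU/kg level, or an inhibitor result. Section 6.1.9 and Flow Chart 9 schedule an inhibitor sample before the first injection of each dosing period and at months 0.5 to 6, but nothing requires that result before the individual dose increase.

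**The concern.** Two rules lead to the same dose, and only one passes through the DMC. A site reading Section 1.4 would conclude that nobody starts 25 IU/kg without DMC agreement. A site reading Section 5.4 would conclude that a patient with two spontaneous bleeds can start at once. Nor can a site tell whether that patient has to be switched.

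Inhibitor formation to FVIII is a primary endpoint and caused the study hold. Cohort 6 was added after the hold, and Section 1.5 gives sequential testing of lower doses as one reason to expect fewer inhibitors. The staging lets the DMC see three patients at 25 IU/kg before the others are exposed to it. An unreconciled second route can remove that look for some patients. It also places in the 25 IU/kg group patients selected by their bleeding, which matters because Section 9.2.3 analyses Cohort 6 by planned daily dose.

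**Working it through.** **Inputs** (Study Outline and Section 3.2): 3 months to the first three patients' follow-up visit; 2 to 3 weeks for results; then further patients start 12.5 IU/kg; after a further 3 months the first three start 25 IU/kg; after another 3 months the rest do. The bleed route opens after 3 months at 12.5 IU/kg. Cohort 6 has 16 evaluable patients: 3 + 13. One week = 12/52 month; DMC review is assumed to take no time beyond the 2 to 3 weeks. Month 0 is the first three patients' first OCTA101 dose.

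**Step 1: reproduce the plan's own duration.**
- Second wave starts 12.5 IU/kg: 3 + 2(12/52) = 3.46 to 3 + 3(12/52) = 3.69.
- First three start 25 IU/kg: 3.46 + 3 = 6.46 to 3.69 + 3 = 6.69, so 6.46 to 6.69 months at 12.5 IU/kg.
- The rest start 25 IU/kg: 9.46 to 9.69, so 9.46 − 3.46 = 6.00 months at 12.5 IU/kg.

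Both fit the stated duration of more than 3 and up to 6-7 months. The planned lead of the first three at 25 IU/kg is 9.46 − 6.46 = 3.0 months.

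**Step 2: apply the bleed-triggered rule.**
- Second-wave patient: earliest 25 IU/kg at 3.46 + 3 = 6.46 to 3.69 + 3 = 6.69. Lead of the first three over this patient: 6.46 − 6.46 = 0. The patient is 3.0 months ahead of the DMC review planned for the second wave.
- First-three patient: the text alone allows month 3.0, which is 3.46 to 3.69 months before the planned DMC-reviewed start. The Study Outline reports that these patients stayed on 12.5 IU/kg during the wait for results, so the window left is the 3.0 months after it.

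**Step 3: vary the timing.** If the further 3 months run from the month-3 visit, the first three start 25 IU/kg at month 6.0 and the lead over a bleed-triggered second-wave patient is 0.46 to 0.69 months. If second-wave patients start later than assumed, the lead grows by the same delay.

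**Step 4: how often could this happen?** The documents give no spontaneous bleeding rate at 12.5 IU/kg, so this is illustration only. With a common Poisson rate and mean m over the interval, P(2 or more) = 1 − e^(−m)(1 + m), and P(at least one of n) = 1 − (1 − p)^n.

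| Assumed spontaneous bleeds per year | At least one of 13 qualifies by month 3 at 12.5 IU/kg | At least one of 13 by month 6 | At least one of the first three by about month 6.6 |
|---|---|---|---|
| 0.5 | 9.0% | 29.5% | 9.1% |
| 1 | 29.5% | 70.7% | 28.4% |
| 2 | 70.7% | 98.1% | 65.7% |
| 4 | 98.1% | about 100% | 95.5% |

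Example, rate 2, month 3: m = 0.5, p = 0.090, 1 − (1 − 0.090)^13 = 0.707. The month-3 column is the chance that the lead can vanish for someone; the month-6 column is the chance that it is at least shortened for someone. Section 7.2.1.1 counts simultaneous sites as separate bleeds, so one spontaneous two-site event can meet the trigger; the Poisson figures ignore this.

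**The case against.** The strongest reply is that the switch is a deliberate individual exception. It stands in the same list as the staged plan, and a 12.5 IU/kg phase of more than 3 months leaves room for it. That may be the intent, but no section says so and Section 1.4 has no carve-out.

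Safeguards do exist. Inhibitors are tested at 0.5 months and monthly (Section 6.1.9) and whenever suspected (Section 7.3.5.2). Safety signals go to the DMC as they arise (Section 8.6), and it meets about every 3 months. One more confirmed inhibitor stops OCTA101 for everyone (Study Outline, Stopping rules). Cohorts 1-3 received 40-60 IU/kg daily, so 25 IU/kg is not a new maximum. All of this stands and limits the risk; none of it acts as a condition before the switch.

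The DMC procedure and the Cohort 6 SAP are separate documents not available here, so either may already address part of this.

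Three stronger readings are tempting but unsupported:
- **That an immediate switch breaks the 2 to 3 week wait.** The Study Outline says "During the 2 to 3 weeks waiting for all relevant results, especially FVIII inhibitor testing results, these patients continued on daily dosing", but that wait precedes the start of further patients on 12.5 IU/kg. It is not a gate on 25 IU/kg, and the Study Outline reports it as past.
- **That a bleed on OCTA101 signals antibodies.** Section 9.2.2 says of Cohorts 1 to 3 "Bleedings occurred only in patients who had developed antibodies or after the end of the daily dosing period"; the Study Outline says "no bleeding rates were calculated, because none occurred during daily prophylaxis with OCTA101". Both can be true, because Section 9.2.2 does not say that the antibody patients were still on OCTA101 when they bled. A link during treatment is not shown, and those cohorts were dosed at 40-60 IU/kg.
- **That the whole cohort could reach 25 IU/kg before the DMC sees any data at that dose.** Even at the highest assumed rate, all 13 second-wave patients qualify with probability 0.264^13, about 3 in 10^8, by month 3 and 0.594^13, about 0.1%, by month 6.

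**Conclusion.** The point holds as a conflict between stated rules on a safety gate. The protocol requires DMC agreement at each stage before 25 IU/kg, describes a second route to that dose without it, and words that route both as required and as optional. For a second-wave patient who qualifies, the 3.0-month lead of the first three falls to about zero, or to 0.5 to 0.7 months on the alternative count. A first-three patient can start ahead of the planned DMC-reviewed date. Patients who do not qualify keep the stagger.

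The timing rests on the protocol's intervals, on second-wave patients starting promptly, and on no added DMC review time. How often it would happen depends on a bleeding rate that the documents do not give. No view is taken on which clinical rule is right.

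**What to change.** Reconcile the Study Outline (Study Design, cohort summary, Duration of Treatment) and Sections 1.4, 3.2 and 5.4 into one rule, worded the same everywhere. It should state:

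1. whether the bleed-triggered switch is required or optional;
2. whether DMC agreement, or DMC release of the 25 IU/kg level, applies to it;
3. whether the result of the inhibitor sample already scheduled before the first injection of each dosing period must be known.

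The content of the rule is for the sponsor and DMC. If an exception is meant, one sentence saying so is enough.

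In the Cohort 6 SAP, flag bleed-triggered switchers in the analyses by planned daily dose and report their inhibitor and LumiTope status at the switch. Separately, clarify whether the statements on bleeds in Cohorts 1-3 in the Study Outline and Section 9.2.2 describe the same events, without presuming that either is wrong.

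Cost: wording changes, one DMC confirmation and a data flag; the samples are already scheduled. If the gates are found to apply, a switching patient may wait a short time.

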### 5.5 Preparation and Method of Administration

OCTA101 and Nuwiq will be provided in single-use vials to be reconstituted in Water for Injection.

Prior to injection, the solution must have reached room temperature, without taking any specific warming-up measures. The preparation should be used immediately after reconstitution. The solution is a clear or slightly opalescent colorless solution. Solutions that are cloudy or have deposits must not be used.

OCTA101 must be injected sc into the abdomen or thigh (see Appendix 1 in Section 13.a). The site of sc administration must be documented. The investigator and the patients will receive detailed Handling Instructions on how and where to perform the sc injections.

Nuwiq must be injected iv by bolus injection (maximally 4 mL/minute) by using aseptic technique.

### 5.6 Blinding, Emergency Envelopes, and Breaking the Study Blind

Not applicable in this open-label study.

# 5.7 Treatment Compliance

### 5.7.1 Drug Dispensing and Accountability

Any IMP provided to the site will be accounted for. This includes IMP received at the site and IMP dispensed to patients. A Drug Inventory and Dispensing Log will be kept current by the Investigator, detailing the dates and quantities of IMP received and dispensed to each patient and the remaining quantity.

For their home treatment, a sufficient amount of OCTA101 and of Nuwiq will be handed out to the patients. The Investigator or his/her designee has to document the date, quantities and batch (lot) number(s) of IMP handed out including the corresponding patient number. The patients will be advised to return used or expired vials to the study site at their on-site visits, and to return used and unused vials at the (early) Termination Visit. Patient returned IMP (used or unused) must not be used anymore and must be destroyed after completion of drug accountability.

The inventory and dispensing log will be available to the monitor to verify drug accountability during the study.

Unused IMP can be destroyed at the study site or returned to the Sponsor for destruction. Destruction can be initiated only after accountability has been verified and fully reconciled by the monitor and after the Sponsor has granted written approval of destruction.

#### 5.7.2 Assessment of Treatment Compliance

Administration of IMP at the study site will be performed by trained personnel, who will document details of administration in the eCRF.

At the first visit, the Investigator will provide eligible patients with a sufficient amount of trial medication (in cooling boxes, if appropriate).

Eligible patients will receive a patient diary after the first injection of OCTA101 (after the first injection of Nuwiq for the run-in in Cohort 6). The investigator will explain to the patient how to fill in the diary and will emphasize the importance of carefully documenting all treatment details, adverse events, and concomitant medications. Furthermore, the efficacy rating criteria for treating a bleeding episode (Section 7.2.1.1) and the criteria for assessing the severity of a bleed will be explained. The Investigator will emphasize the necessity of careful documentation of all treatment details. The recording of at-home injections will include the date and time, dose, and batch number. IMP is provided with tear-off labels that must be placed in the diary.

In case of treatment of BEs, the patients will document the site and severity of the bleed, the start and end dates and time, and carry out an efficacy assessment according to the explanation provided in the diary. The patients will be trained on how to administer Nuwiq to control bleeding, if required.

Study product administrations that are overseen by the Investigator (e.g. treatment in case of severe BEs treated at the study site), are to be documented in the patient's journal (by the Investigator), as well as in the patient's diary (by the patient).

In addition, the patient will record any concomitant medications taken during the study period in their diaries.

For each follow-up visit at the study site, the patients must bring all diaries to be reviewed and validated by site personnel.

# 6 STUDY CONDUCT

The flow charts of assessments by study visit are given, starting on page 21. The flow chart of the recently ongoing Cohort 6 can be found on page 26.

